2.2.2 Storage and transportation conditions – Mexico to Germany

The test supplies will be kept in their original packaging and in a secure storage area with restricted access, in line with the recommended storage conditions (labelled). It is recommended to transport and store probes such as swabs and Salivette® Cortisol at 4-8°C.

For storage times of longer than 48 hours prior to shipment of swab and Salivette® Cortisol samples for storage in Germany, transportation at temperatures < 20°C in dry ice is recommended.

Packaging of all shipments must comply with the international regulations for transporting dangerous goods (UN3373 for dry ice).

2.2.3 Responsibility for the *in vitro* diagnosis

Only the documented authorised staff may receive and dispense *in vitro* diagnostic tests. These tests must be performed as stated in the product instructions or in the test protocol.

The occupational health care team must keep records of the diagnostic tests entering the test site, the site's inventory, use with each participant and the disposal of compromised devices.

All compromised devices will be disposed of locally by the test site. The receipt, use and disposal of the devices must be duly documented. Any discrepancies must be reported.

2.3 REFERENCE MEASURES

2.3.1 Restrictions

There are no dietary or lifestyle restrictions in place. However, a condition for taking biological samples is that no food or medicinal products may have been consumed for a period of at least 30 minutes before the procedure to prevent saliva contamination.

2.3.2 Handling of swabs and saliva samples

The throat swab sample collected arrives in a transport medium. The swabs are washed within the transport media, by shaking the tubes for 10 minutes at approximately 500 rpm, in an orbital shaker at room temperature. The sample can be stored for up to 7 days in the transport medium, at +4°C. The saliva samples collected with Salivette® Cortisol are packaged in the corresponding primary container.

3. SAMPLE SIZE

There is no calculated sample size but rather a general attempt to directly compare swab samples versus saliva samples collected with Salivette® Cortisol in a participant, with a minimum of 20 to 80 participants.

4. ADVERSE EVENT REPORTING

Although this study is based on recently collected data, adverse event (AE) collection is not required. There is no Boehringer Ingelheim medicinal product intended or marketed for this disease. The investigator is encouraged to report all adverse events related to any product marketed by Boehringer Ingelheim, in accordance with the local regulatory requirements for spontaneous AE reporting at the investigator's discretion using the locally established means and AE report forms. The term AE includes the exposure to medicinal products during pregnancy and, regardless of whether or not an AE occurs, any abuse, off-label use, misuse, medication error, occupational exposure, lack of efficacy and unexpected benefit.

Other reports. As any reportable adverse events involving medical devices, technical complaints regarding the product and device deficiencies could cause harm to patients during clinical studies related to Salivette® Cortisol/swabs, the investigator will remain responsible for managing all activities, including reporting the medical device in line with the local regulatory requirements on reporting medical devices.

According to its definition, a reportable adverse event involving a medical device means any unfavourable medical event, disease or injury, or any unfavourable clinical sign, including abnormal laboratory findings, in subjects, users or other individuals, in the context of a clinical study, regardless of whether or not it is related to the investigational device, and which meets the criteria for a reportable event as set forth in the applicable laws and regulations.

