1.4 RISK-BENEFIT ASSESSMENT

The Salivette® Cortisol device, which is placed in the mouth and gently chewed for approximately 60 seconds, is considered to be very low risk. Its taste may be considered unpleasant. It is handled by the participant and, as such, there is no additional risk expected for the medical staff. During the tests, everyone wears masks in the rooms while the swab samples are taken, and the medical staff are protected with FFP2 masks, protective clothing and double gloves. Sampling with Salivette® Cortisol can be performed on-site. The layout of the room will follow the general distancing and hygiene measures in place, and surfaces will be cleaned and disinfected in line with procedure after each participant leaves. The risk of harm, such as sequelae due to the medical procedure, and the risk of infection of all participants, including the occupational health care team, was assessed before the tests and was considered highly unlikely.

There is recent evidence (Wyllie, AL et al. 2020. <https://doi.org/10.1101/2020.04.16.20067835doi>) that saliva sampling potentially produces more reliable results when compared to swab sampling.

Conclusions: It is considered necessary to establish sampling methods other than swab samples in order to reduce the biosafety risk and increase the flexibility of tests and their acceptance among potentially infected individuals, as taking swab samples is more invasive than collecting samples with Salivette® Cortisol. The sampling method established should allow for regular tests and be easy and well accepted by patients, while providing comparable results.

Risks and methods related to the medical procedure

There are some risks involved in the nasopharyngeal mucosa sampling procedure using swabs, such as mild bleeding of the nasal mucosa, pharyngeal pain after the sample is taken, sneezing, cough, and gag reflex when taking the pharyngeal mucosa sample. There are no known risks for patients related to the Salivette® Cortisol device, and even accidental ingestion of the device has not led to any adverse reactions being reported, as it is made of inert material and does not contain any active or reactive substances.

[figure not shown]
Sample taking with swab/Salivette® Cortisol

SARS-CoV-2 sampling:

The nasopharyngeal mucosa swab samples and those taken with the Salivette® Cortisol device will be collected in line with the SARS-CoV-2 biological sample collection standards in place at the Research Site.

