2.1.3 Inclusion criteria

Only participants who meet the following criteria will be included in the programme:

1. Informed consent form signed and dated before any samples have been taken.
2. Suspected or confirmed SARS-CoV-2 infection by PCR within the past five days.
3. Male and/or female patients aged 18 years and over.

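### Section 4 waives adverse event collection for prospectively taken swab and saliva samples, so the device-reporting duty has no capture step and expected minor sampling effects are not systematically recorded

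*Combined protocol and SAP*

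**What the plan says.** Section 4 (Adverse event reporting) opens with "Although this study is based on recently collected data, adverse event (AE) collection is not required". The next sentence reads "There is no Boehringer Ingelheim medicinal product intended or marketed for this disease". Two reporting routes follow:

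- **Spontaneous route.** "The investigator is encouraged to report all adverse events related to any product marketed by Boehringer Ingelheim". This is at the investigator's discretion and limited to the sponsor's own marketed products.
- **Device route (the Other reports paragraph).** For Salivette® Cortisol and the swabs, "the investigator will remain responsible for managing all activities, including reporting the medical device in line with the local regulatory requirements". The definition that follows covers untoward events in participants, users or others whatever their relation to the device, but only those that meet the legal criteria for reportability.

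Elsewhere the protocol describes prospective sampling. Section 2.1.3 requires "Informed consent form signed and dated before any samples have been taken". The Sampling instructions in section 1.4 set out swab and saliva collection step by step and say that the oropharyngeal swab will probably provoke a cough. The risk text in section 1.4 lists, for swab sampling, "mild bleeding of the nasal mucosa, pharyngeal pain after the sample is taken, sneezing, cough, and gag reflex". For the saliva device it states "There are no known risks for patients related to the Salivette® Cortisol device", apart from a taste that some may dislike.

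**The concern.** Participants undergo two procedures because they joined the programme, and the protocol itself foresees effects from one of them. A waiver of event collection needs a reason that applies to those procedures, and section 4 does not clearly give one.

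Two things are at stake. First, the investigator has a duty to report certain device events, yet no step in the protocol prompts anyone to note an event so that it can be assessed. Second, section 1.4 supports the saliva device partly on low risk, lesser invasiveness and acceptance by patients. Each participant gives both specimens, but the plan would yield no systematic information on how either was tolerated.

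**Working it through.** The plan gives no event rate, safety threshold or calculated sample size, so there is no figure to reproduce. The check sets the sections side by side.

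1. **Is the sampling prospective?** Yes. Section 2.1.3 places consent before any sample, and section 1.4 gives the collection steps for both specimens.

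2. **What reason supports the waiver?** The opening sentence of section 4 begins with *although*, which is concessive: it sets the waiver against the recent collection of data and does not derive the waiver from it. If the clause means freshly collected data, it fits section 2.1.3 but supplies no reason for a waiver. If it means data that already existed, it conflicts with sections 1.4 and 2.1.3. The remaining reason is the absence of a sponsor medicinal product for the disease, which has no bearing on a swab or a saliva device.

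3. **Which events have a route?**

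| Type of event | Route in section 4 | Step for noting it |
|---|---|---|
| Related to a sponsor-marketed product | Spontaneous, discretionary | None |
| Swab or Salivette® Cortisol event meeting legal criteria | Investigator responsible under local device rules | None |
| Expected sampling effect not meeting legal criteria | None | None |

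4. **Is there a capture step elsewhere?** Section 2.2.3 requires records of the receipt, inventory, use and disposal of diagnostic tests and devices, not of what happens to participants. The statistical methods entry in the protocol summary covers only a descriptive comparison of test results.

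5. **Which foreseen effects fall in the last row?** Throat pain, cough and gag reflex, where they are not legally reportable. Nasal bleeding is less certain. Section 1.4 attaches it to nasopharyngeal sampling, whereas the Sampling steps and section 2.2.1 describe oropharyngeal or throat swabs.

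6. **Illustration only.** If events were recorded and none occurred, the exact two-sided 95% upper limit would be 1 − 0.025^(1/n):
   - n = 20: 1 − 0.025^(1/20) = 0.168, or 16.8%.
   - n = 80: 1 − 0.025^(1/80) = 0.045, or 4.5%.

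   No decision in the plan rests on these limits. Zero events is also an unlikely result for the swab, since the protocol expects cough.

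**The case against.** The strongest defence is that section 4 describes two separate regimes. The first paragraph deals with the sponsor's medicinal products, for which routine collection has little purpose. The Other reports paragraph deals with devices and keeps the reporting duty in force. An investigator can report a qualifying event without a systematic form. The objective is diagnostic comparability, no safety or tolerability aim is stated, and the risk assessment was completed before testing began, so no planned conclusion depends on event data.

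Much of this stands, and it rules out three stronger readings that a reader might infer:

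- **That the waiver rests on a false claim of using existing data.** The wording is concessive and never mentions secondary use. It is ambiguous, but it does not clearly contradict the consent criterion.
- **That all sampling harms would go unrecorded.** Legally reportable swab and Salivette® Cortisol events remain the investigator's responsibility.
- **That the trial's main result is compromised.** The comparison of PCR results does not use event data.

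The defence does not close the gap. The device definition disregards relation to the device, so events must be noticed and noted before anyone can judge whether they are reportable. The section opens by saying that collection is not required, and the two-regime reading has to be supplied by the reader. Foreseen effects below the legal threshold have no route under either regime.

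**Conclusion.** The point holds in a limited form. Section 4 states a waiver whose only clear reason does not apply to the procedures performed. It assigns a device-reporting duty without a step for capturing events, and it leaves expected non-reportable sampling effects without systematic recording. This reaches every participant (20 to 80) and both specimens.

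Severity is low. The foreseen effects are mostly minor, and the diagnostic comparison is untouched. No event rate can be given, because the plan would produce none. The conclusion assumes that no recording form or site procedure outside the document already captures these events, and that at least some of the listed effects fall below the local threshold for reportability, which the protocol does not specify.

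**What to change.** 1. Reconcile section 4 with sections 1.4 and 2.1.3 on whether events at sampling are recorded.
2. Clarify or delete the clause about recently collected data.
3. Replace the waiver with one form entry per specimen at the single sampling visit, for any event during or just after collection of the swab and of the Salivette® Cortisol sample. The investigator can then judge reportability from a written record.
4. List these events descriptively by specimen where attribution is possible. No test or threshold is needed. If zero-event limits are shown at all, mark them as illustrative.

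The cost is a short change to the protocol text and one form line per specimen at a visit that already takes place. The downsides are a little extra recording by site staff and imperfect attribution: both specimens are taken at the same visit, so later throat pain, for example, may not be assignable to either one.
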